## 9. Study Endpoints

### 9.1 Primary

**Virologic clearance:** Clearance and/or reduction in viral RNA from day 1 to day 10, as determined by PCR and/or quantitative real time PCR. Thus, the presence of virus from any sample will be scored as positive on that day and the number of copies will be compared to evaluate virus clearance with each therapy. Time until virus becomes undetectable.

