**Synopsis**

Product provided by:	BiogenIdec Inc.
Investigational Product/ Drug Product:	Interferon beta-1a (IFN $\beta$ -1a)
Title of the Study:	A Pilot Study to Evaluate the Safety and Efficacy of IFN $\beta$ -1a in the Treatment of Patients Presenting with Ebola Virus Illness.
Development phase:	I/II
Sponsor-Investigator:	[name] [name]
Collaborator:	[name]
Planned Study Period:	January/February 2015 to April/May 2015
Primary Objective:	To evaluate the effectiveness of IFN $\beta$ -1a on viremia in peripheral blood
Primary Endpoint:	Viral load reduction/clearance: Reduction and/or clearance in copies/mL of viral RNA from day 1 to day 14 and, if applicable, 30 days after the last dose
Secondary Objectives:	To evaluate the safety of IFN $\beta$ -1a in the treatment of Ebola virus disease
Secondary Endpoints	
Occurrence and severity of adverse event; time to onset from the initial dose, duration (number of days), severity, and seriousness of solicited and non-solicited injection site reactions and systemic adverse events occurring up to 7 days after the last injection. Occurrence, nature, time to onset from the initial dose, duration, severity, relationship to injection of SAEs throughout the trial, and up to 30 days post-treatment.
 
The frequency of clinically important (moderate or severe) adverse events will be compared between the IFN <math>\beta</math>-1a treatment group and the group receiving usual standard of care.
 
The frequency of serious adverse events will be compared between the groups.

Tertiary Objectives	
To evaluate the effect of IFN <math>\beta</math>-1a therapy on preventing Ebola virus disease progression and/or on resolution of disease.
 
To assess effects on disease symptoms and survival.

Tertiary Endpoints	
Clinical improvement will be evaluated by comparing the following parameters between the groups:
 
Days in treatment centre
 
Days of symptom manifestation: hemorrhage (as IFN <math>\beta</math>-1a may cause fever, myalgia, sore throat, headache, nausea, vomiting, and diarrhea similar to that associated with ebola virus infection, these adverse events will be recorded but not used in the analysis of efficacy).

	Death – all causes for study duration

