
Statistical Methods and Analyses
	
Endpoints will be described and compared between baseline and day 10, for the treatment group using cross-tabulation tables and Fisher's Exact test for categorical variables, t-test for normally distributed continuous variables, and Wilcoxon non-parametric test for non-normally distributed continuous or ordinal variables. Data collected will be compared with a retrospective analysis of age-matched Ebola-infected individuals who presented with similar symptoms (and viral loads) and who did not receive IFN <math>\beta</math>-1a.

	
Safety variables such as fever will be considered in three different formats:
 

1. As ordinal, representing various levels of severity of the AE. For instance, fever will be described as “none”, “mild”, “moderate” or “severe”.

2. As binary, considering only the presence vs. the absence of the AE.

3. As binary, considering the most serious expression of the AE. For instance by grouping “moderate” and “severe” together.

 
Separate analyses for time periods of 0-3, 4-7 and 8-10 days will be conducted. For each of these time periods the most severe report of the AE for each participant will be counted.
 
Adverse Events and Serious Adverse Events will be considered in two ways: presence of any event and presence of any event related to the treatment.
 
Viral clearance and symptom endpoints will be analyzed as binary variables for detection (presence) or non-detection (absence) as well as continuous variables where applicable (e.g.; quantitative RT-PCR measurements).

--	---

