## 10.2 Statistical analyses and methods

Demographics, and underlying conditions will be described by means and standard deviation for continuous variables, by median and interquartile range for ordinal or count variables, and by frequencies and percentages for categorical variables. Endpoints will be described and compared between treatment and usual standard of care groups using cross-tabulation tables and Fisher's Exact test for categorical variables, t-test for normally distributed continuous variables and Wilcoxon non-parametric test for non-normally distributed continuous or ordinal variables.

Safety variables such as fever will be considered in three different formats:

1. As ordinal, representing various levels of severity of the symptom. For instance, fever will be described as "none", "mild", "moderate", or "severe".
2. As binary, considering only the presence vs. the absence of the symptom.
3. As binary, considering the most serious expression of the symptom. For instance by grouping "moderate" and "severe" together.

Separate analyses for time periods of 0-3, 4-7, and 8-10 days will be conducted. For each of these time periods the most severe report of the AE for each participant will be counted.

Adverse Events and Serious Adverse Events will be considered in two ways: presence of any event and presence of any event related to the treatment.

Symptoms will be assessed as a repeated measure using GEE modelling.

Survival will be analyzed using a Kaplan-Meier curve and Cox-proportional hazard modeling with 2 week and 1 month survival rates determined.

Viral clearance will be analyzed as binary variables for detection (presence) or non-detection (absence) as well as continuous variables where applicable (e.g. quantitative RT-PCR measurements).

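### Time to undetectable virus, part of the primary endpoint, is left to t-test or Wilcoxon with no rule for patients who never clear; a clearers-only comparison could lose most of its power

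*Protocol*

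**What the plan says.** Section 9.1 of the protocol builds the primary endpoint from three pieces. Two are in one phrase, "Clearance and/or reduction in viral RNA from day 1 to day 10, as determined by PCR and/or quantitative real time PCR", and the third is "Time until virus becomes undetectable".

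Section 10.2 then assigns methods by type of endpoint. Group comparisons use Fisher's exact test for categorical variables and "t-test for normally distributed continuous variables and Wilcoxon non-parametric test for non-normally distributed continuous or ordinal variables". It names separate methods for particular outcomes: GEE for symptoms, and for mortality "Survival will be analyzed using a Kaplan-Meier curve and Cox-proportional hazard modeling with 2 week and 1 month survival rates determined". Virology has its own sentence: "Viral clearance will be analyzed as binary variables for detection (presence) or non-detection (absence) as well as continuous variables where applicable". No time-to-event method is attached to time to clearance, and no value or rank is given for a patient who never clears.

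Two synopsis entries differ from the body. The primary endpoint there reads "Reduction and/or clearance in copies/mL of viral RNA from day 1 to day 14 and, if applicable, 30 days after the last dose", against day 10 in section 9.1. The statistical paragraph says "Endpoints will be described and compared between baseline and day 10, for the treatment group", whereas section 10.2 compares treated patients with usual care.

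**The concern.** Time to clearance is right-censored. A patient still PCR-positive at the last sample, or one who dies positive, has no observed time. The protocol makes such patients foreseeable:

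- Section 9.1 stops at day 10.
- Section 6.5 expects missing data points.
- Section 1.1 cites a fatality of 57-90%.

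A t-test cannot use these patients without an invented value. Wilcoxon can use them only if they are given a rank, and none is specified. The default in most software is to analyse the recorded times, which means clearers only. That answers how fast clearance was among those who cleared. The primary objective asks whether the drug reduces viremia in everyone treated. A drug that mainly turns non-clearers into clearers would show little on the clearers-only scale.

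The synopsis does not supply a way out. A baseline-to-day-10 comparison cannot be applied to a time to clearance, which has no baseline value.

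**Working it through.** **No figure to reproduce.** The protocol gives no alpha, power, effect size or clearance rate, and section 10.1 presents 30-50 as a feasibility number. Every input below is an assumption: 30 patients per group, daily sampling, a day-10 cut-off, two-sided 5% tests and no deaths unless stated.

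**Step 1: one case by hand.** Take exponential clearance times with 40% of controls and 70% of treated patients clear by day 10.

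- Rates: λ = −ln(1−p)/10. Control −ln(0.6)/10 = 0.0511; treated −ln(0.3)/10 = 0.1204. Hazard ratio 0.1204/0.0511 = 2.36.
- Mean time among clearers: 1/λ − 10(1−p)/p. Control 19.58 − 15.00 = 4.58 days; treated 8.31 − 4.29 = 4.02 days. Difference 0.56 day.
- Mean time over the 10 days with everyone kept (restricted mean): p/λ. Control 0.4/0.0511 = 7.83; treated 0.7/0.1204 = 5.81. Difference 2.02 days.
- Share of the restricted-mean difference seen among clearers: 0.56/2.02 = 28%.

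**Step 2: power by simulation.** Weibull times with shape 1 or 2, rounded up to whole days; Fisher by exact calculation.

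| Day-10 clearance, control vs treated | t-test or Wilcoxon, clearers only | Log-rank, all patients | Wilcoxon, non-clearers ranked worst | Fisher, cleared by day 10 |
|---|---|---|---|---|
| 30% vs 60% | 5-7% | 65-67% | 62-63% | 56% |
| 40% vs 70% | 8-9% | 67-70% | 65-67% | 56% |
| 50% vs 80% | 11-12% | 75-76% | 70-72% | 60% |

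With 3,000 replicates the standard error at 70% power is √(0.7 × 0.3/3000) = 0.8 point, so runs differ by a point or two. In round terms: 6-12% for clearers only, 66-74% for log-rank, 63-71% for worst-rank Wilcoxon.

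**Step 3: how far this depends on the assumptions.**

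- Exponential times, hazard ratio 1.5-3, control clearance 30-70%: the clearers-only difference keeps 22-49% of the restricted-mean difference.
- Normally distributed times shifted by 2-3 days: 33-49% of the shift is kept when 25-50% of controls clear, but 63-77% when 75-84% clear.
- Hazard ratio 2, 25 per group, 95-99% of controls clear: 43-53% power for clearers only against 62-64% for log-rank.
- Step 2 models with a longer window: clearers-only power is 16-73% at day 20 and 31-87% at day 30. At day 30 with shape 2 it is 75-87%, against 88-94% for log-rank.
- Deaths added (50% of controls, 30% of treated; 25 per group, hazard ratio 2, 50% underlying control clearance): about 4-6% for clearers only, against 51% for log-rank with deaths kept as non-clearers.

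**The case against.** A reader might infer that the protocol drops everyone still positive and that the primary endpoint therefore loses most of the drug effect. The documents do not support that.

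- **No exclusion is stated.** Section 10.2 allows Wilcoxon for ordinal data. Ranking non-clearers last fits that rule, keeps everyone and recovers most of the log-rank power. This stands: the clearers-only analysis is one reading of an incomplete rule. It is still true that the protocol does not choose the safer reading.
- **The cleared versus not-cleared contrast is itself planned.** The binary analysis with Fisher's exact test has 56-60% power in the same scenarios, and copy numbers are also compared. Both keep still-positive patients. This stands and confines the problem to one component.
- **Day-10 censoring is not settled.** The synopsis extends the endpoint to day 14 and possibly 30 days after the last dose, and section 6.5 foresees weekly and 30-day follow-up. This stands in part: a longer window reduces the loss. However, sparse late samples place clearance only within an interval, which again calls for a stated method.
- **This is a feasibility pilot, and a SAP may value the non-clearers.** This lowers the weight. It does not remove the point, because section 10.2 already assigns methods outcome by outcome and reserves time-to-event methods for survival.

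A reader might also suspect that a clearers-only comparison could reverse the sign of the effect. None of the scenarios computed here shows that: the difference among clearers is small but in the right direction.

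**Conclusion.** The point holds in a limited form. A right-censored component of the primary endpoint falls under tests that have no value for non-clearers, while the suitable method sits in the same section for survival only. If only observed clearance times are analysed, power is about 6-12% against 66-74% for log-rank, given 30 per group, no deaths, a day-10 cut-off and control clearance of 30-50% against 60-80% treated. The loss is modest if nearly all controls clear, smaller with a longer window, and largely absent with a worst-rank Wilcoxon. The protocol does not settle which of these applies. The binary and copy-number analyses of the primary endpoint are unaffected. The change is worth making because the component is primary and the correction is nearly free.

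**What to change.** Add to section 10.2, in substance:

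- Time to first undetectable blood PCR is analysed as a time-to-event endpoint in all patients with a positive baseline PCR.
- Living patients who are still positive are censored at their last PCR.
- Death while positive is a competing event (cumulative incidence), or counts as non-clearance through the end of the window. It is not ordinary censoring, which would assume that those who died would have gone on to clear like the survivors. That is untenable at the fatality cited in section 1.1.
- A t-test or Wilcoxon restricted to clearers is not used for this endpoint.

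Reconcile the primary window (day 10 in section 9.1, day 14 and possibly later in the synopsis), since it sets the censoring date. Also state in the synopsis that the baseline-to-day-10 comparison does not apply to this component.

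Cost: a few sentences, methods the protocol already uses or a close relative of them, and no new data.

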### 9.2 Secondary

**Safety:** Occurrence and severity of adverse event; time to onset, duration (number of days), severity, and seriousness of solicited and non-solicited injection site reactions and systemic adverse events occurring up to 7 days after the last injection. Occurrence, nature, time to onset relative to the first IFN  $\beta$ -1a dose, duration, severity, relationship to injection of SAEs throughout the trial.

- The frequency of clinically important (moderate or severe) adverse events will be compared between the groups
- The frequency of serious adverse events will be compared between the groups.

Parameters to look for adverse events will be solicited such as local injection site erythema and swelling, fever, heart rate, blood pressure, and rash.

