## 1. Introduction

### 1.1 Background on Ebola Virus Infection

Clinical Ebola hemorrhagic fever is characterized by onset of fever, headache, myalgia, fatigue and gastrointestinal distress, 2-21 days post exposure to virus. Immune responses play a critical role in Ebola virus (EBOV) pathogenesis: infection is associated with an early loss of lymphocytes and down-regulation of interferon production and actions. There is subsequent dysregulation of coagulation, leading to clinically important hemorrhage in a minority of patients. The genus *ebolavirus* includes 5 different viruses: Sudan virus, Tai Forest virus, EBOV, Reston virus and Bundibugyo virus. EBOV has the highest fatality rate – 57-90%. Data from human infections with EBOV are limited, but the evidence from previous outbreaks suggests that the innate immune response is predictive of outcome. Specifically, an early and transient pro-inflammatory cytokine response, including IFN- $\alpha$ , is associated with survival, yet a sustained and increasing pro-inflammatory cytokine response, with dendritic cell infection that abrogates the IFN response, is associated with death (1, 2). Notably, in the absence of a robust innate immune response, including IFN- $\alpha$  activation of dendritic cells, the adaptive immune response (B and T cell activation) is severely impaired, leading to failure of control of viral replication and poor outcome.

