### 8.3 Adverse Event Definitions and Reporting

Adverse Event (AE): is any untoward medical occurrence in a patient or clinical investigation participant administered a product. It does not necessarily have to have a causal relationship with this treatment. An AE can therefore be any unfavorable and unintended sign (including an abnormal laboratory finding, for example), symptom or disease temporally associated with the use of a medicinal product, whether or not considered related to the medicinal product.

All adverse events will be recorded and transcribed into the CRF. Solicited AEs and non-solicited AEs will be collected daily for the first four days and then every 2-3 days during therapy, or whenever reported by patients. SAEs will be collected while on study medication and for 30 days after administration of the last dose.

**Serious Adverse Event (SAE):** is any adverse event that:

- is fatal
- is life-threatening
- results in persistent or significant disability/incapacity
- requires initial hospitalization or prolongation of existing hospitalization
- causes congenital anomalies or birth defects

The term "life-threatening" refers to an event in which the patient was at risk of death at the time of the event. It does not refer to an event, which hypothetically might have caused death, if it were more severe. All deaths occurring while on protocol therapy or within 30 days of the last dose, should be reported (see below).

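### The between-group SAE comparison counts Ebola deaths and life-threatening Ebola as SAEs, so it is largely a second mortality comparison; fatal and non-fatal SAEs should be compared separately

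*Protocol*

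**What the plan says.** Protocol section 8.3 defines an adverse event broadly: "It does not necessarily have to have a causal relationship with this treatment". An event is serious if, among other criteria, it is fatal, "is life-threatening", or "requires initial hospitalization or prolongation of existing hospitalization". No section exempts Ebola death or Ebola progression. Deaths on therapy or within 30 days of the last dose are reportable whatever their cause.

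Section 9.2 makes SAE frequency a between-group safety endpoint: "The frequency of serious adverse events will be compared between the groups". Section 10.2 fixes the summary: "Adverse Events and Serious Adverse Events will be considered in two ways: presence of any event", and second, presence of any event related to treatment. Categorical endpoints are compared by Fisher's exact test. Section 8.4 also describes a direct safety comparison of treated with untreated patients. It mentions attribution to the intervention, but it is unclear whether that qualifier covers SAEs or only moderate and severe adverse events.

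Section 1.1 puts fatality at 57-90%. Table 1 gives 1214 deaths among 2047 cases in Guinea, the trial country. All-cause death is already a tertiary endpoint (section 9.3), with Kaplan-Meier and Cox analyses (section 10.2). Section 16 names safety as a determining factor for extending the study.

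**The concern.** Each patient is scored once, so a patient who dies of Ebola counts the same as one with serious interferon toxicity. In a disease this lethal, most patients in both groups are positive before any drug event can register. Two consequences follow. Serious non-fatal toxicity is diluted, because it changes the score only in patients who would otherwise have had no SAE. The contrast also moves with mortality: if interferon works, any-SAE can fall in the treated group while the drug causes serious harm, and a larger sample would not cure that. The same deaths are analysed again as survival, so the safety comparison adds little independent information.

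**Working it through.** The protocol states no power and no derived sample size for this comparison, so there is no figure to reproduce.

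**Inputs from the protocol.** Fatality d = 57% to 90% (section 1.1); crude ratio for Guinea 1214/2047 = 59.3% (Table 1); 30-50 patients (section 10.1); Fisher's exact test (section 10.2).

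**Assumptions.** Two-sided 0.05; equal groups of 30 or 50 (comparator size is not stated); deaths fall inside the SAE window; background serious events b = 5%; interferon causes a serious event in h = 20%, independently of death; equal fatality in both groups unless stated.

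**1. Any-SAE as written**

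Usual care: 1 − (1 − d)(1 − b). Interferon: 1 − (1 − d)(1 − b)(1 − h).

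| d | Usual care | Interferon | Power, 30 / 50 per group |
|---|---|---|---|
| 57% | 1 − 0.43×0.95 = 59.2% | 1 − 0.43×0.95×0.80 = 67.3% | 5.9% / 9.5% |
| 75% | 76.3% | 81.0% | 3.7% / 5.7% |
| 90% | 90.5% | 92.4% | 0.9% / 2.2% |

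At 57% fatality, deaths make up 0.57/0.592 = 96% of usual-care patients with an SAE and 0.57/0.673 = 85% of interferon patients with one. At 40% fatality, a case more favourable to the plan, power is still only 9% / 17%.

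These rates leave out life-threatening Ebola in survivors. If half the survivors had it (d = 57%, no other background), the rates would be 78.5% v 82.8%, with power 3.3% / 5.1%.

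**2. Direction**

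Suppose interferon also cuts fatality from 60% to 45%. Usual care: 1 − 0.40×0.95 = 62.0%. Interferon: 1 − 0.55×0.95×0.80 = 58.2%. The treated group shows fewer SAEs although one patient in five has a serious toxic event.

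**3. The same toxicity counted apart from Ebola events**

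- Observable in every patient: b v 1 − (1 − b)(0.80).
- Seen only in survivors (d = 57%, b = 5%): 0.43×0.05 = 2.2% v 0.43×0.24 = 10.3% of all patients.

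| Case | Rates | Power, 30 / 50 per group |
|---|---|---|
| All patients, b = 5% | 5% v 24% | 40% / 71% |
| All patients, b = 20% | 20% v 36% | 20% / 35% |
| All patients, b = 30% | 30% v 44% | 13% / 24% |
| Survivors only, b = 5% | 2.2% v 10.3% | 4.7% / 19.8% |

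Higher backgrounds are plausible because section 1.1 says Ebola itself causes lymphocyte loss and disordered coagulation, which overlap with the blood-count harms in section 2.3.1.

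**4. The treatment-related analysis**

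Untreated patients cannot have an interferon-related SAE. The between-group version is therefore zero by construction on one side. Within the treated group it rests on attribution, which section 8.2 concedes may be difficult.

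**The case against.** The strongest reply is that any-SAE is one of several safety summaries. Section 10.2 also plans a treatment-related analysis. Section 9.2 records nature, onset, duration, severity and relationship for each SAE and compares moderate or severe adverse events between groups. Section 10.2 also analyses adverse events by period. This stands: a reader might infer that the plan cannot show serious interferon harm at all, and the documents do not support that. Such harm can be described within the treated group. What these provisions do not supply is a between-group comparison of serious harm that is free of the death count.

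A second reply is that all-cause counting is conventional and avoids attribution. That also stands, so any-SAE should not be replaced. Removing Ebola progression from the comparison would be wrong too: section 8.1 treats interferon-worsened progression as a harm of interest, and labelling a death as due to Ebola is itself an attribution.

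A third reply is that the low power reflects pilot size. This stands in part. A reader might take 40-71% as what a separate count delivers, but that needs toxicity visible in patients who die and only 5% background. If it is seen only in survivors, there is no gain at 30 per group. The reversal of direction does not depend on sample size.

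Finally, 90% is the upper end of a general range, Guinea's crude ratio is 59%, and suspect cases may enrol (section 5.3). The conclusion already holds at 57%, and dilution is still marked at 40%.

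**Conclusion.** The point holds as a should-fix. On the protocol's own definitions, the between-group any-SAE comparison is dominated by death. At 57% fatality, a 20% serious toxicity shifts it by about 8 percentage points (59% to 67%) with power of roughly 6-10%, and a mortality benefit can make interferon look safer than it is. Fatality comes from the protocol; the toxicity and background rates, their independence from death, the significance level and equal group sizes are assumptions.

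The gain from separating the counts is real but uncertain: about 40-71% power in the favourable case, 13-20% (30 per group) or 24-35% (50 per group) with 20-30% background, and about 5-20% if harm is seen only in survivors. The firmer benefit is interpretability: a fall in deaths would no longer be able to mask serious toxicity in a single combined count.

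A reader might infer that the extension decision turns on this test. The documents do not say so. Section 10.1 describes a feasibility pilot, section 16 names safety without a rule, and the stopping rule in section 8.4 concerns a death from an SAE judged related to the product.

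**What to change.** Keep collecting and reporting every SAE, and keep the any-SAE summary. In sections 9.2 and 10.2, make the between-group safety comparison in two parts:

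- **Fatal SAEs:** all-cause death, read together with the survival analysis.
- **Non-fatal SAEs by type:** the interferon harms named in sections 2.3.1 and 8.2 as a pre-set group, and Ebola progression as its own category. Class both by one written rule applied identically in the two groups, without relying on investigator attribution.

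State that non-fatal counts are affected by early death, and give the risk among patients still alive or per patient-day. Present the treatment-related SAE analysis as a description of the interferon group only, and clarify in section 8.4 whether the attribution qualifier applies to SAEs.

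The cost is wording, a short term list and slightly more tabulation, using data the protocol already plans to collect. Some multiplicity is added, so with this sample size the split comparisons are best read as estimates with intervals.
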